APPENDIX V GANTT CHART

APPENDIX VI PUBLICATION POLICY

AUTHORSHIP POLICY

1. PRINCIPLES OF AUTHORSHIP

The following principles of authorship have been derived from editorial publications from leading journals (see references) and are in accordance with the rules of the International Committee of Medical Journal Editors.

a. Group authorship

Group authorship will be appropriate for some publications, such as main reports. This will apply when the intellectual work underpinning a publication has been carried out by a group, and no one person can be identified as having substantially greater responsibility for its contents than others'. In such cases the authorship will be presented by the collective title - The PROSPECT Trial Group - and the article should carry a footnote of the names of the people (and their institutions) represented by the corporate title. In some situations one or more authors may take responsibility for drafting the paper but all group members qualify as members; in this case, this should be recognised using the byline 'Jane Doe and the Trial Group'. Group authorship may also be appropriate for publications where one or more authors take responsibility for a group, in which case the other group members are not authors but may be listed in the acknowledgement (the byline would read 'Jane Doe for the Trial Group').

b. Individual authorship

Other papers, such as describing satellite studies, will have individual authorship. In order to qualify for authorship an individual must fulfil the following criteria¹:

- i. Each author should have participated sufficiently in the work represented by the article to take public responsibility for the content.
- ii. Participation must include three steps:
- conception or design of the work represented by the article OR analysis and interpretation of the data OR both; AND
- drafting the article or revising it for critically important content; AND
- final approval of the version to be published.

Participation solely in the collection of data is insufficient by itself and those persons who have contributed intellectually to the article but those contributors do not justify authorship may be acknowledged and their contribution described.¹

c. Determining authorship

Tentative decisions on authorship should be made as soon as possible.¹ These should be justified to, and agreed by, the Project Management Group. Any difficulties or disagreements will be resolved by the Steering Committee.

2. AUTHORSHIP FOR PUBLICATION ARISING FROM PROSPECT

a. Operationalising authorship rules

We envisage two types of report (including conference presentations) arising from the PROSPECT trial and its associated projects:

- i. Reports of work arising from the main PROSPECT trial If all grant-holders and research staff fulfil authorship rules, group authorship should be used under the collective title of 'The PROSPECT Trial Group'; if one or more individuals have made a significant contribution above and beyond other group members but where all group members fulfil authorship rules, authorship will be attributed to 'Jane Doe and the PROSPECT Trial Group'.
- ii. Reports of satellite studies and subsidiary projects Authorship should be guided by the authorship rules outlined in Section 1 above. Grant-holders and research staff not directly associated with the specific project should only be included as authors if they fulfil the authorship rules. Grant-holders and research staff who have made a contribution to the project but do not fulfil authorship rules should be recognised in the Acknowledgement section. The role of the PROSPECT Trial Group in the development and support of the project should be recognised in the Acknowledgement section. The lead researcher should be responsible for ratifying authorship with the Project Management Group.

For reports which specifically arise from the PROSPECT trial but where all members do not fulfil authorship rules (for example, specialist sub-study publications), authorship should be attributed to 'Jane Doe for the PROSPECT Trial Group'. If individual members of the group are dissatisfied by a decision, they can appeal to the Management Group for reconciliation. If this cannot be achieved, the matter should be referred to the Steering Group.

b. Quality assurance

Ensuring quality assurance is essential to the good name of the trial group. For reports of individual projects, internal peer review among members of the Project Management Group is a requirement prior to submission of papers. All reports of work arising from the PROSPECT trial including conference abstracts should be peer reviewed by the Project Management Group.

## Study Design

PROSPECT is a multi-centred randomised control trial with a parallel-cohort design. The aim of the study is to investigate the safety, effectiveness and cost-effectiveness of operations for women with pelvic organ prolapse. The study includes two RCTs within a Comprehensive Cohort Study, with the following principle objectives:

In women having a primary prolapse repair, the effects of a standard repair versus the following:

- 1) Standard repair using a biological graft inlay
- 2) Standard repair using a non-absorbable or combined mesh inlay

In women having a secondary prolapse repair, the effects of a standard repair versus the following:

- 3) Standard repair using a non-absorbable or combined mesh inlay
- 4) Mesh kit procedure

Treatment allocation is minimised by age (>60/60+), type of planned prolapse surgery (anterior/posterior/both), concomitant continence procedure and concomitant prolapse procedure. Treatment allocations are summarised in Figure 1.

[figure not shown]

Figure 1. Treatment allocation in PROSPECT RCTs

Since recruitment began, additional randomisation menu options have been made available, partly as a result of some mesh types being unavailable on

certain days. It is possible in RCT1 to randomise just between standard repair and non-absorbable mesh (RCT1B), or between standard repair and biological mesh (RCT1C). In the secondary trial, an additional menu option of randomising between standard repair and mesh kit has been added (RCT2D).

At close of recruitment (August 2013), there were 36 participating centres throughout the UK. The centres are listed in Table 1.

**Table 11**– PROSPECT participating centres

Aberdeen	Cumbria	Maidstone	Rotherham
Ayrshire & Arran	Derby	Manchester	South Devon
Barnsley	Exeter	Mid Yorkshire	South Tees (Friarage)
Birmingham	Harrogate	Middlesex	South Tees (James Cook)
Bolton	Huddersfield	North Devon	Sunderland
Bradford	Hull	Nottingham	Taunton
Brighton	Imperial	Plymouth	Whipps Cross
Bristol	Leicester	Portsmouth	Wolverhampton
Chester	Luton & Dunstable	Preston	York

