If the new prolapse is in a different compartment (de novo) and the original site does not require revision surgery, the woman will be classed as having a **primary** repair of the de novo prolapse and randomised in the primary trial.

Randomisation will be minimised on:

- age (less than 60 years or 60 and over);
- type of prolapse being randomised (anterior, posterior or both);
- need for a concomitant incontinence procedure (e.g. TVT) or not;
- need for a concomitant upper vaginal prolapse procedure (e.g. hysterectomy, cervical amputation, vault repair) or not;
- surgeon.

2.4 Ensuring standardisation of intervention and outcome measurement (avoiding performance bias)

All gynaecologists will agree to perform the prolapse surgery using the agreed and standardised methods, materials and procedures as detailed in the Standard Operating Procedures. Both specialist urogynaecologists and general gynaecologists will be eligible for recruiting and randomising women, thus extending the generalisability of the trial and facilitating the future transfer of skills. All the staff delivering the surgical intervention and measuring the objective outcomes will receive

training to ensure standardisation and consistency of their surgical techniques and measurement of pre-operative and post-operative prolapse parameters.

All staff will be proficient in performing the POP-Q⁵ method of objective quantification of prolapse descent used pre- and post-operatively. Suitably qualified and trained research Recruitment Officers (rather than clinical staff with direct responsibility for patient care) will be responsible for ensuring that these are carried out and recorded independently before and, for randomised women, at 12 months after surgery. The POP-Q assessments will be recorded on standard study forms or using the POP-Q grid (Appendix III). Data from these forms will be entered using the internet based PROSPECT database and paper copies collected and stored centrally at the Study Office in Aberdeen.

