6.3 Statistical analysis

A single principal analysis is anticipated at 12 months after the last woman is recruited. The Data Monitoring Committee will determine the frequency of confidential interim analyses, but at present these are planned on four occasions during the data collection period.

All analyses within the RCT will be based on the intention-to-treat principle. All outcomes in both trials will be described with the appropriate descriptive statistics where relevant: mean and standard deviation for continuous and count outcomes, or medians and inter-quartile range if required for skewed data, numbers and

percentages for dichotomous and categorical outcomes (for example subjective recurrence of prolapse).

Analysis of the primary outcome (POP-SS) will estimate the mean differences (and 95% confidence interval) between the intervention and control groups using a general linear model that adjusts for the minimisation covariates and other important prognostic covariates, including the baseline symptom score, at 12 months after surgery. A similar analysis will be used to analyse the primary outcome at 6 and 24 months.

All secondary analyses will be analysed in a similar manner but using the appropriate generalised linear model (for example logistic regression for dichotomous data such as subjective prolapse failure, Poisson or negative binomial regression for count data such as number of nights in hospital) or time to event methods (e.g. Cox regression on time to further surgery) where required. We will explore analysing outcomes at all time points simultaneously using for example, Generalised Estimating Equations or Generalised Linear Latent and Mixed Models, and relevant link functions, to explore changes in outcome over time.

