### **Primary/Secondary Outcomes**

Outcomes at 12 months will be analysed using a generalised linear model which will adjust for minimisation and baseline covariates. The development of treatment effects over time will be explored using repeated measures mixed effects models that make use of available outcome data at each time point, e.g. 6, 12 and 24 months for the POP-SS (this assumes outcome data missing at random conditional on the observed covariates).

Furthermore, it is anticipated that many women may be asymptomatic one year after surgery and their POP-SS will be zero. A composite binary/linear model will be used to analyse the primary outcome (POP-SS at 12 months) so that a distribution of POP-SS with a high proportion of zero values is taken into account. The binary element will be based on a POP-SS=0, and the linear element will treat the POP-SS score as a continuous measure with possible values ranging from 0 to 28.

The menu design of the trials will be taken into account in the analyses of all outcomes. Both RCTs have 3 strata, as shown in Table 2 and Table 3.

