**Table 3: Number of participants randomised to each stratum in the secondary RCT**

Stratum	Standard repair (A)	Synthetic mesh (B)	Mesh kit (C)
RCT2	24	24	44
RCT2B	31	28	n/a
RCT2D	1	n/a	3

In the primary RCT, RCT1 will be analysed on its own and treatment effects for treatments B and C (compared with A) will be estimated. In addition, the RCT1 and RCT1B strata will be combined (using just data in arms A and B) in a separate model to create a further estimate of the treatment effect between A and B. Similarly, the RCT1 and RCT1C strata will be combined (using just data in arms A and C) in a separate model to create a further estimate of the treatment effect between A and C. Where strata are combined, the stratum variable will be fitted as a fixed effect in the model. The secondary trial will be similarly analysed, although RCT2 will not be combined with RCT2D due to the small number randomised to RCT2D.

Secondary outcomes will be analysed in a similar fashion to the primary outcome using appropriate link functions.

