## Sample Size and Power Calculation

In an average population of women having prolapse surgery, about 70% will be having a primary procedure. Two comparisons will be made:

- a standard repair versus a standard repair using a biological graft inlay; and
- a standard repair versus a standard repair using a non-absorbable or combined mesh inlay.

Pilot data have shown that a conservative estimate of the standard deviation of the primary patient-reported outcome POP-SS is 8 units. A difference in means of 2 units would represent an improvement in the response to a POP-SS question, for example, a feeling of something coming down or in the vagina, from 'Most of the Time' to 'Occasionally'. To detect a standardised difference of 0.25 with 90% power and alpha equal to 0.025 (to maintain the nominal p value at 0.05 with two tests being used), we would need to randomise 400 women to each arm of the study. Best efforts using evidence based techniques will be employed to maximise the response rate at follow up. Nevertheless, we feel it prudent to inflate the estimated sample size for 15% dropout at one year requiring approximately 1450 women having primary surgery to be recruited to the trial. Adjusting for baseline covariates and minimising the loss to follow up will potentially improve this power. A trial of this size would also be adequately powered to detect important differences in the economic and secondary outcomes.

It is estimated that the other 30% of women requiring anterior and/or posterior repair will receive a secondary or subsequent repair. Therefore, during the proposed time period required for recruiting 1450 women to the primary repair RCT above, it is anticipated approximately 620 women having secondary surgery will be eligible and will be willing to be randomised. Within the secondary RCT two comparisons will be made:

- a standard repair versus a standard repair using a non-absorbable or combined mesh inlay; and

- a standard repair versus a mesh kit procedure.

It would be possible to detect with 90% power and alpha equal to 0.025 a standardised effect size of 0.38 which equates to 3 points on the POP-SS scale (this estimated effect detectable has been calculated adjusting for potential 15% dropout at one year). The pilot data from IMPRESS indicated that women having secondary repairs have a higher level of symptoms at baseline. Therefore it is biologically plausible that these women may show a larger benefit from the options available.

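### The SAP's list of minimisation factors leaves out surgeon, which the Protocol includes, so it is unclear whether and how surgeon enters the adjusted models

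*SAP*

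**What the plan says.** Protocol 2.3 introduces its list with "Randomisation will be minimised on" and names five items: age band, compartment(s) being randomised, a concomitant incontinence procedure, a concomitant upper vaginal procedure, and surgeon.

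The SAP's Study Design says "Treatment allocation is minimised by age (>60/60+), type of planned prolapse surgery (anterior/posterior/both), concomitant continence procedure and concomitant prolapse procedure". That is the first four items. Surgeon is absent.

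On the model, the SAP (Primary/Secondary Outcomes) says "Outcomes at 12 months will be analysed using a generalised linear model which will adjust for minimisation and baseline covariates", and gives no list of those covariates. The one further design term it names is the randomisation-menu stratum: "Where strata are combined, the stratum variable will be fitted as a fixed effect in the model". Nothing in the SAP gives surgeon or centre a fixed or random term. Protocol 6.3 specifies a "general linear model that adjusts for the minimisation covariates and other important prognostic covariates", including the baseline symptom score. Read with Protocol 2.3, that takes in surgeon.

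**The concern.** The two documents imply different primary models. The Study Design list is the only place where the SAP says what the minimisation factors are. An analyst working from the SAP alone would therefore fit four factors, and one working from the Protocol would fit five.

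There is reason to expect some variation between surgeons. Appendix I, section 1.3 of the Protocol says that operative technique differs a good deal between gynaecologists. Section 2.4 admits both specialists and generalists, and section 3.1 lets the surgeon's preference and ability influence the mesh chosen.

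When allocation is balanced on a prognostic factor, the treatment contrast is largely free of that factor's variation. If the model leaves the factor out, its variance stays in the residual. The reported standard error then exceeds the true one, the interval is too wide and the test rejects too seldom. The form of the term also matters, since omitting it, fitting fixed effects and fitting a random intercept give different intervals. With the SAP silent, that choice could be made after the data are seen.

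**Working it through.** **Inputs from the SAP.** SD of POP-SS 8 ("a conservative estimate of the standard deviation of the primary patient-reported outcome POP-SS is 8 units"); difference 2 units; "To detect a standardised difference of 0.25 with 90% power and alpha equal to 0.025"; 400 women per arm; 95% intervals; 5% significance level. Table 2 gives the numbers randomised.

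**Assumed, because the documents give no figure.** Share of POP-SS variance lying between surgeons (ICC): 0 to 0.10, with total SD held at 8.

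**1. The plan's own figure.** n per arm = 2 × (2.241 + 1.282)² × (8/2)² = 398, against 400 stated. It reproduces with two-sided alpha 0.025, and surgeon plays no part in it. At 400 per arm, SE = 8 × √(2/400) = 0.566, the half-width is 1.96 × 0.566 = 1.109, and power is Φ(2/0.566 − 2.241) = 90.2%.

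**2. Effect of omitting a perfectly balanced surgeon factor.**
- Reported SE ÷ true SE = 1/√(1 − ICC)
- True size of a nominal 5% test = 2 × [1 − Φ(1.96/√(1 − ICC))]
- Power with surgeon fitted = Φ(2/(0.566 × √(1 − ICC)) − 2.241)
- Power with surgeon omitted = Φ(2/(0.566 × √(1 − ICC)) − 2.241/√(1 − ICC))

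| ICC | Half-width, omitted | Half-width, fitted | Excess width | True size of 5% test | Power, omitted | Power, fitted |
|---|---|---|---|---|---|---|
| 0 | 1.109 | 1.109 | 0% | 5.0% | 90.2% | 90.2% |
| 0.01 | 1.109 | 1.103 | 0.5% | 4.9% | 90.3% | 90.5% |
| 0.02 | 1.109 | 1.098 | 1.0% | 4.8% | 90.4% | 90.8% |
| 0.05 | 1.109 | 1.081 | 2.6% | 4.4% | 90.8% | 91.7% |
| 0.10 | 1.109 | 1.052 | 5.4% | 3.9% | 91.4% | 93.1% |

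The design figure of 90.2% takes no account of balance on surgeon. Under balance the unadjusted test itself gains a little, so the gain from fitting surgeon is at most 93.1 − 91.4 = 1.7 points.

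**3. Numbers as randomised.** For standard repair against biological mesh, Table 2 gives 253 + 116 = 369 and 255 + 114 = 369. With the planned 15% loss, power is 81.3% at ICC 0. At ICC 0.05 it is 81.9% omitted and 83.4% fitted; at 0.10 it is 82.6% and 85.5%.

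**4. Imperfect balance.** Minimisation was simulated with 740 women, 65 surgeons and allocation probability 0.8 (the last two assumed). Against a random surgeon intercept with the ICC taken as known, omitting surgeon gave standard errors too large by 0%, 0.3%, 0.7%, 2.0% and 4.4% at the five ICCs. The figures in step 2 are therefore upper bounds.

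**5. Fixed effects instead.** With 65 surgeons as fixed effects, the mean SE was as follows.

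| ICC | Surgeon omitted | 65 fixed effects |
|---|---|---|
| 0 | 0.588 | 0.601 |
| 0.02 | 0.587 | 0.594 |
| 0.05 | 0.587 | 0.585 |
| 0.10 | 0.587 | 0.569 |

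Fixed effects widen the interval at low ICC and help only once the ICC is above about 0.05.

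**The case against.** The SAP's Study Design is a summary and not a covariate list. The model sentence names no factors, so it could be read as covering every factor actually used, surgeon included. That reading is open, but it then conflicts with the SAP's own list, and it still leaves fixed or random effects unspecified.

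A reader might infer that surgeon was certainly balanced and that the planned intervals are certainly too wide. The documents support neither. Protocol 2.3 is prospective. The SAP was written with recruitment closed and the randomised counts in hand, and neither document says which list the algorithm used. If surgeon was not in the algorithm, the argument from balance falls away. A run of the simulation without surgeon in the minimisation (ICC 0.05) gave a rejection rate of 5.1% with surgeon omitted, and adding surgeon to the SAP list would then be a false statement. Excess width also needs an ICC above zero, and the documents give neither an ICC nor a number of surgeons.

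The effect is also small and in the safe direction. The 90% target is met at 400 per arm without surgeon. The menu stratum, fitted where strata are combined, may absorb some surgeon variation, because it partly reflects what a surgeon could randomise between. All of this stands, and it limits the point to a discrepancy with a modest, conditional cost.

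**Conclusion.** The mismatch between Protocol 2.3 and the SAP's Study Design is plain on the page, and the SAP does not settle whether surgeon enters the model. The consequence is conditional. If surgeon was used in allocation and predicts POP-SS, omitting it costs at most 5.4% in interval width and 1.7 points of power at 400 per arm, over an assumed ICC up to 0.10. If the ICC is zero it costs nothing.

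A reader might go on to infer a biased treatment effect or too many false positives. Neither follows for the POP-SS mean difference, where the error is conservative. The figures apply to a linear mean difference only. They do not carry over to the binary part of the SAP's composite model or to other odds ratios, where leaving out a prognostic factor also moves the estimate towards 1.

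This should be put right before analysis, but it does not threaten the trial's validity.

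**What to change.** First check the randomisation system, then make both lists match the algorithm as implemented.

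- **If surgeon was used:** add it to the SAP's list and pre-specify a random surgeon intercept in the models for POP-SS and other continuous outcomes. Do not use many fixed effects. Name a fallback for non-convergence or very small surgeon groups (centre in place of surgeon, or no term), which will matter mainly in the secondary trial. Say also whether surgeon enters the binary part of the composite model and the binary secondary outcomes.
- **If surgeon was not used:** correct the Protocol list instead, and have the SAP say that surgeon is not a minimisation covariate.

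In either case, list the adjustment covariates by name in the SAP. The cost is a query to the randomisation system and a line or two of text. If surgeon was a minimisation factor, the data are already held. The drawback is a slightly more complex model that may occasionally fail to converge.

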## Outcome Measures

All outcome measures are recorded at baseline, 12 months and 24 months.

## Primary Outcomes

The primary patient-reported outcomes are symptoms of prolapse, measured as:

- the number and frequency of prolapse symptoms on the Pelvic Organ Prolapse Symptom Scale (POP-SS) at one year after surgery
- a quality of life outcome measured as the overall effect of prolapse symptoms on everyday life.

The POP-SS is a composite outcome measure comprising seven patient recorded items each relating to a different symptom. Each item has an ordinal response schedule with five levels of response based on frequency of the symptom (“never”, “occasionally”, “sometimes”, “most of the time” and “all of the time”) and is scored from 0 to 4 respectively. The overall POP-SS score is the sum of each item score and can range from zero to 28.

For the primary analysis, individual items that are missing will be assumed to have a value of zero. However, this assumption will be tested in sensitivity analyses. If all seven questions are unanswered, then the POP-SS score will be treated as missing.

The primary economic outcome measure of cost effectiveness is incremental cost per QALY (QALYs based on the EQ-5D). The cost effectiveness analysis is set out separately in the economic analysis plan.

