### **Imputation**

Imputation of missing baseline data (collected prior to randomisation) will be undertaken in order to reduce bias. Although no imputation of missing participant-level outcome data will be carried out in the main analysis of the primary outcome, imputation of instruments (e.g. POP-SS) will be undertaken at item-level according to the rules of the specific instrument.

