## **Sensitivity analyses**

It is recommended that sensitivity analyses are carried out where there are missing outcome data. For the primary outcome POP-SS at data 12 months we will explore the impact of missing data on the complete-case treatment estimates and confidence intervals by using multiple imputation and pattern mixture modelling methods depending on level and patterns of missing data.

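### Scoring blank POP-SS items as 'never' in the primary analysis can only lower scores and can create false symptom-free women; the item-level rule should be changed and fully specified

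*SAP*

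**What the plan says.** The SAP (Primary Outcomes) defines POP-SS as seven symptom items, each with five frequency levels from 'never' to 'all of the time', which "is scored from 0 to 4 respectively". It adds: "The overall POP-SS score is the sum of each item score and can range from zero to 28".

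For blank items the same section says: "For the primary analysis, individual items that are missing will be assumed to have a value of zero". The only limit is: "If all seven questions are unanswered, then the POP-SS score will be treated as missing". It calls the rule an assumption and continues: "However, this assumption will be tested in sensitivity analyses".

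Three other places bear on this:

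- **SAP, Imputation:** participant-level outcomes are not imputed in the main analysis, but "imputation of instruments (e.g. POP-SS) will be undertaken at item-level according to the rules of the specific instrument". Those rules are not given.
- **SAP, Sensitivity analyses:** the effect of missing 12-month POP-SS on the complete-case estimate will be explored "by using multiple imputation and pattern mixture modelling methods depending on level and patterns of missing data". Blank items are not mentioned.
- **SAP, Primary/Secondary Outcomes:** many women are expected to score zero at one year, so a composite binary/linear model is planned for the primary outcome. "The binary element will be based on a POP-SS=0".

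**The concern.** A blank is given the best possible answer and then treated as if the woman had given it. One answered item out of seven is enough for a total to count as observed.

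The rule acts on the primary outcome twice. It lowers the mean score whenever a skipped symptom was in fact present. It can also turn a symptomatic woman into a zero, which is the event in the binary element of the composite model.

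The promised sensitivity analysis leaves the headline estimate as it is. If multiple imputation is applied to totals, a partly completed form already has a total, so the filled zeros would pass through as observed data. Nor does the SAP say whether zero-scoring is the instrument's own rule, so two analysts reading the two sections could score the same form differently.

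**Working it through.** **Inputs from the documents.** Seven items scored 0 to 4 (SAP, Primary Outcomes). Target difference 2 points, SD 8, 90% power, alpha 0.025, 400 per arm, 15% dropout, about 1450 women (SAP, Sample Size and Power Calculation; Protocol 2.7.2, where Table 1 gives 483 per arm after dropout).

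**Assumed, because the documents are silent.** The share of items left blank, *m*, from 1% to 10%; 12-month arm means between 3.2 and 6.4; a true difference of 2.0.

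1. **The plan's own figure.** With two-sided alpha, n = 2(z₀.₉₈₇₅ + z₀.₉₀)² / (2/8)² = 2(2.241 + 1.282)² / 0.0625 ≈ 397.2, so 398 per arm against the stated 400. Power at 400 is 90.2%. Dropout gives 400/0.85 = 471 per arm and 3 × 471 = 1413, close to 483 and 1450. These figures are not in dispute; they serve as the yardstick.

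2. **Direction.** Recorded score = true score − sum of the true values of the blank items. Each of those values lies between 0 and 4, so the error cannot be upward. It is nil only if every skipped item was truly 'never'. One blank whose true answer was 'sometimes' (2) lowers that woman's score by 2.

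3. **Random blanks, equal in both arms.** Each arm mean is multiplied by (1 − *m*), and so is the difference.

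| Items blank (*m*) | Fall in arm mean (*m* × 3.2 to *m* × 6.4) | Difference, 2.00 × (1 − *m*) | Power at 400 per arm, SD kept at 8 |
|---|---|---|---|
| 1% | 0.03 to 0.06 | 1.98 | 89.6% |
| 2% | 0.06 to 0.13 | 1.96 | 88.9% |
| 5% | 0.16 to 0.32 | 1.90 | 86.8% |
| 10% | 0.32 to 0.64 | 1.80 | 82.7% |

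If the SD shrinks in the same proportion as the means, power stays at 90.2%.

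4. **Random blanks, unequal by arm (5% and 2%).** With true means 6.42 and 4.42, more blanks in the higher-scoring arm gives 6.42 × 0.95 − 4.42 × 0.98 = 1.77. More blanks in the lower-scoring arm gives 6.42 × 0.98 − 4.42 × 0.95 = 2.09. The difference can move either way.

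5. **Skipping that depends on the answer, 5% blank, equal by arm.** These results come from a simulation of seven correlated 0–4 items with 200,000 women per arm.
   - Symptomatic items four times as likely to be skipped: the arm mean falls by 0.35 to 0.53.
   - 'Never' items four times as likely to be skipped: it falls by 0.05 to 0.12.
   - Only 'never' items skipped: zero-scoring is exact, and prorating from the answered items overstates the mean by 0.12 to 0.15.

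6. **False zeros, same simulation.** At 5% blank at random, the share with POP-SS=0 rises by about 0.6 to 0.9 percentage points. At 10% blank with symptomatic skipping, the largest rise is about 4 points (0.405 to 0.448).

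7. **Does prorating remove false zeros?** Seven times the mean of the answered items is zero exactly when every answered item is zero. That is the same condition as under zero-filling, so prorating alone changes no one's zero status.

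**The case against.** The SAP states the assumption openly, promises to test it and treats wholly blank forms as missing. No item non-response rate is given, and at 1% to 2% blank the difference moves only from 2.00 to 1.98 or 1.96. If women leave blank the symptoms they do not have, zero-scoring is right and prorating is wrong. All of this stands. It limits the size of the point and is a good reason to keep zero-filling as a sensitivity analysis. It does not justify an extreme, one-directional default as the primary rule when the pattern of skipping is unknown.

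Four stronger readings are tempting and are not supported:

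- **That the comparison between arms is biased by a differential effect.** Equal random blanks only attenuate the difference. A spurious or exaggerated effect needs skipping to differ by arm, and nothing in the documents shows this. Age is a minimisation factor (Protocol 2.3), other baseline traits are balanced on average by randomisation, and women are not told their operation unless they ask (Protocol 2.6).
- **That one woman's loss can be set against the 2-point target.** A single blank can remove 2 points from one score, but the target is a difference in group means.
- **That the Primary Outcomes and Imputation sections contradict each other.** If zero-scoring is the instrument's rule, they agree. The SAP does not say, so the defect is an unstated rule rather than a proven conflict.
- **That prorating cures the problem.** It restores the mean under random blanks but leaves the false zeros (steps 3 and 7).

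**Conclusion.** The concern holds in a limited form. The primary scoring rule errs in one direction only, needs just one answered item, and feeds both the mean score and the POP-SS=0 element of the composite model. The planned check names no item-level method, so as written it does not settle the matter.

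With random blanks equal by arm, the effect on a true 2.0-point difference is attenuation to 1.98 at 1%, 1.90 at 5% and 1.80 at 10% of items blank. These rates are assumptions, as are the arm means and item correlations behind the false-zero figures. At low rates the effect is small. This is a worthwhile and cheap correction to the primary analysis, but it does not show that the trial's conclusions would be wrong.

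**What to change.** 1. **Reconcile the two SAP sections.** State the instrument's missing-item rule in Primary Outcomes and Imputation, and say whether zero-scoring is that rule.
2. **Change the primary rule.** Use item-level multiple imputation from the answered items (or prorating), with a stated minimum number of answered items below which the total is missing. The documents give no basis for a particular minimum, so the trial team should choose and justify it before analysis. Amend the Imputation section to allow this. Totals below the minimum would then be missing in the main analysis, because the SAP currently reserves participant-level imputation for sensitivity analyses. Keep zero-filling as a named sensitivity analysis.
3. **Protect the binary element.** Count POP-SS=0 only when all seven items are answered 'never', or derive it from the item-level imputations.
4. **Be consistent and report.** Apply the same rule to the baseline score, and tabulate blank items by arm and time point so that the attenuation and any imbalance can be judged.

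The cost is SAP wording and a few lines of code. The downside is that a few women with very few answered items move from observed to missing in the primary analysis.
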